5.4.2. Analysis Methods

Exploratory time to event variables will be analyzed descriptively only for apalutamide group. KM method will be applied to graphically describe the distribution. Median event times, the 6-month,

1-year and 2-year event free rates, as appropriate, and their 2-sided 95% confidence intervals will be provided.

SAFETY

Safety data will be analyzed using safety analysis set. The safety parameters to be evaluated are the incidence, intensity, and type of adverse events (AE), vital signs, ECG, and clinical laboratory results.

Unless otherwise specified, no statistical inference will be performed in analyzing the safety data.

In this study, control group subjects without distant metastasis will switch to treatment with apalutamide plus ADT after completion of 5 cycles of placebo + ADT treatment (handling by the IWRS). Subjects who have documented PSA progression prior to completion of 5 cycles of study treatment, will cross over to apalutamide at the time of PSA progression. As such, safety data will be presented by the following treatment groups as appropriate.

Placebo ^a	Apalutamide	Placebo to Apalutamide b	Apalutamide Treated ^c

^a Placebo subjects treated with Placebo + ADT before cross-over

6.1. Adverse Events

Subjects will be assessed for adverse events while on the study. Adverse events (AEs) will be graded according to the NCI Common Terminology Criteria for Adverse Events (CTCAE) version 4.03 and coded to preferred term and system organ class (SOC) using the MedDRA version 20.0 or later. All AEs reported on or after the date of first dose until 30 days (inclusive) after the last dose of study drug will be considered treatment-emergent and will be summarized by treatment group.

For each treatment group, AE incidence rates will be summarized with frequency and percentage by SOC and preferred term, with all subjects treated in that treatment group as the denominator, unless otherwise specified. In addition, AE incidence rates will also be summarized by severity and relationship to study drug. Treatment-related AEs are those judged by the Investigator to be at least possibly related to the blinded study drug. AEs with missing severity or relationship to study drug will be classified as severe and treatment-related, respectively. Subjects with multiple occurrences of events will only be counted once at the maximum severity to study drug for each preferred team, SOC. Deaths that occur within 30 days after the last dose of study drug are defined as on-study deaths.

Summary tables of the following AEs will be provided:

Overall summary of AEs: the number and percentage of subjects who experienced any AE including COVID-19, number of subjects with Grade 3/4 AEs, any serious adverse event

22

^b Placebo subjects treated with apalutamide + ADT after cross-over

^c Subjects treated with apalutamide + ADT including subjects from original apalutamide arm and subjects crossed over from placebo arm

(SAE) including COVID-19, any treatment-related AE, treatment related Grade 3/4 AE, any treatment-related SAE, AE leading to treatment discontinuation including COVID-19, related AE leading to treatment discontinuation, AE leading to death including COVID-19, related AE leading to death, and all deaths within 30 days of last dose

- All AEs by SOC and preferred term
- All AEs by SOC, preferred term, and toxicity grade
- Grades 3 or 4 AEs by SOC and preferred term
- Grades 3 or 4 AEs by decreasing frequency of preferred term
- Treatment-related AEs by SOC and preferred term
- Treatment-related AEs by SOC, preferred term, and toxicity grade
- Treatment-related AEs by decreasing frequency of preferred term
- Treatment-related Grades 3 or 4 AEs by SOC and preferred term
- Treatment-related Grades 3 or 4 AEs by decreasing frequency of preferred term
- All AEs that led to death by SOC and preferred term
- All AEs that led to study drug discontinuation by SOC and preferred term. Study drug discontinuation will be determined from the End of Treatment CRF (where reason for termination is "Adverse Event") and the specific AE will be determined from the AE eCRF page (where action taken is "Drug Withdrawn")
- All AEs that led to study drug discontinuation by SOC, preferred term, and toxicity grade
- All AEs that lead to study drug dose modification by SOC and preferred term
- All SAEs by SOC and preferred term
- All SAEs by SOC, preferred term, and toxicity grade
- Deaths will be summarized by time period (on-study vs. during follow-up) and cause of death Subject listings of all Grades 3 or 4 AEs, all SAEs, AEs that led to study drug discontinuation, dose modification, and all deaths will be provided as well.

Narratives will be written for the following subjects in the final clinical study report:

- Subjects who die ≤ 30 days after the last dose of study drug
- Subjects who discontinue study drug due to adverse events
- Subjects who have a serious adverse event
- Subjects who experience a seizure
- Grade 3 or higher adverse events of special interest

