9.3.2. Safety Analyses

Participants who receive at least 1 dose of study drug will be analyzed for safety. The safety parameters to be evaluated are the incidence, intensity, and type of AEs, vital signs measurements, and clinical laboratory results. Exposure to study drug and reasons for discontinuation of study treatment will be tabulated.

Adverse Events

The verbatim terms used in the eCRF by investigators to identify AEs will be coded using the Medical Dictionary for Regulatory Activities, Version 21.0 or later. and will be graded according to the NCI-CTCAE, Version 4.03. Treatment-emergent AEs are AEs that occur or worsen on or after first dose of study drug through 30 days after the last dose of study drug. All reported intervention-emergent AEs will be included in the analysis. For each AE, the percentage of participants who experience at least 1 occurrence of the given event will be summarized by intervention group. In addition, comparisons between intervention groups will be provided if appropriate.

Treatment-emergent AEs will be summarized by system organ class, preferred term, toxicity grade, and relationship to study drug. Serious adverse events and deaths will also be summarized. Summaries, listings, datasets, or participant narratives may be provided, as appropriate, for those participants who die, who discontinue intervention due to an AE, or who experience a severe or a SAE.

Clinical Laboratory Tests

Laboratory data will be summarized by type of laboratory test. Descriptive statistics will be calculated for each laboratory analyte at baseline and for observed values and changes from baseline at each scheduled time point. A listing of participants with any laboratory results outside the reference ranges will be provided. A listing of participants with any markedly abnormal laboratory results will also be provided. Normal ranges will be used to identify values that are outside the normal ranges and abnormal laboratory results will be graded according to the NCI-CTCAE Version 4.03. A shift summary of baseline grade by maximum post-baseline CTCAE grade will be presented. For each laboratory parameter, the baseline laboratory value will be defined as the last laboratory value collected on or prior to the date of the first dose of study drug. Participants who develop toxicities of Grade ≥3 will be listed.

Electrocardiogram

Electrocardiogram data will be summarized by ECG parameter at screening (baseline) only.

Vital Signs

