1.1. Trial Objectives

Primary Objectives:

To compare the improvement in time to prostate specific antigen (PSA) progression (TTPP, as defined by Prostate Cancer Working Group 2 [PCWG2]) of apalutamide versus placebo in Chinese subjects with high risk NM-CRPC.^[1]

Secondary Objectives:

- To evaluate the safety and tolerability of apalutamide
- To compare the prostate-specific antigen (PSA) response rate in Chinese subjects with high risk NM-CRPC treated with apalutamide versus placebo
- To evaluate the pharmacokinetics (PK) of apalutamide

Exploratory Objectives:

- To evaluate the metastasis-free survival (MFS) of Chinese subjects with high risk NM-CRPC treated with apalutamide
- To evaluate the overall survival (OS) of Chinese subjects with high risk NM-CRPC treated with apalutamide
- To evaluate the time to symptomatic progression in Chinese subjects with high risk NM-CRPC treated with apalutamide

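### Crude adverse-event percentages set about 140 days of placebo at most beside 5 to 37 months of potential follow-up on apalutamide, so for persisting risks they mix drug effect with time on drug

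*SAP*

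**What the plan says.** **Measure.** SAP 6.1 states that "AE incidence rates will be summarized with frequency and percentage by SOC and preferred term, with all subjects treated in that treatment group". Those subjects form the denominator, with room for exceptions. Protocol 9.3.2 agrees: "For each AE, the percentage of participants who experience at least 1 occurrence of the given event will be summarized by intervention group". It adds that "comparisons between intervention groups will be provided if appropriate".

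**Columns.** The introduction to the SAP's safety section defines Placebo as "Placebo subjects treated with Placebo + ADT before cross-over". Apalutamide, Placebo to Apalutamide, and a pooled Apalutamide Treated group have their own columns. Placebo ends at documented PSA progression or after 5 cycles of 28 days. Apalutamide continues until distant metastasis, unacceptable toxicity or the end of the study (SAP 1.2).

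**Risk window.** SAP 6.1 counts AEs from first dose, and those "until 30 days (inclusive) after the last dose of study drug will be considered treatment-emergent". There is no cut-off common to the two arms.

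**Status.** The safety objective is "To evaluate the safety and tolerability of apalutamide", and in general "no statistical inference will be performed in analyzing the safety data". Exposure is tabulated by treatment group in SAP 4.4 but is not used to adjust any AE figure.

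**The concern.** A crude percentage rises with time at risk. Where one column is observed for a few months and the other for up to three years, an AE with a steady background rate shows a higher percentage in the longer column whether or not the drug contributes. For an AE that the drug does raise, the crude contrast exaggerates the increase.

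The randomised placebo period is this study's only internal control for background AEs in men on ADT, and protocol 2.1 describes the safety data as a comparison with placebo. The sponsor knows the problem: for the earlier global study, protocol 2.2 reports median exposures of 32.9 and 11.5 months (ratio 2.9) and then says which AEs remained more frequent after exposure adjustment. No such step is planned here. At stake is how the AE tables are read, not the efficacy result.

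**Working it through.** **Inputs from the documents**
- Accrual 32 months plus 5 months of follow-up (protocol 9.1, SAP 1.4). The plan's own figure reproduces: 32 + 5 = 37 months. Potential follow-up is 5 months for the last participant dosed and 37 for the first.
- Placebo cap T = 5 × 28 = 140 days; 140/30.4375 = 4.60 months.
- Placebo TTPP exponential with median 3.7 months: L = ln 2/3.7 = 0.187 per month.
- PSA drawn 7 days before the Cycle 3, 4 and 5 visits, so that a switch can take place at the visit (Schedule of Activities, footnote 8).
- 75 participants randomised 2:1, so about 25 on placebo.

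**Assumptions, not in the documents**
- Constant AE hazard h = 0.005 to 0.05 per month, equal in both arms (no drug effect).
- Discontinuation d = 0.01 to 0.03 per month in both arms. As a rough check, the 32.9-month median apalutamide exposure in the earlier study, read as exponential, gives ln 2/32.9 = 0.021.
- Uniform accrual.

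**Step 1: placebo time.** Progression by Day 49, 77 or 105 leads to a switch at Day 56, 84 or 112; everyone else switches at Day 140. With F(t) = 1 − exp(−Lt), the shares are 26.0%, 11.7%, 9.9% and 52.4%. Mean time before discontinuation = (0.260 × 56 + 0.117 × 84 + 0.099 × 112 + 0.524 × 140)/30.4375 = 3.57 months. About 0.524 × 25 = 13 participants would reach the fifth cycle on placebo.

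**Step 2: expected percentages.** With k = h + d:
- Apalutamide: (h/k) × [1 − (exp(−5k) − exp(−37k))/(32k)]
- Placebo: (h/k) × (1 − exp(−ks)), averaged over the switch times s of Step 1, or with s = T if all complete 5 cycles

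| h | d | Apalutamide | Placebo, visit-based | Ratio | Placebo, all 5 cycles | Ratio |
|---|---|---|---|---|---|---|
| 0.005 | 0.01 | 8.77% | 1.74% | 5.06 | 2.22% | 3.95 |
| 0.01 | 0.02 | 14.89% | 3.37% | 4.42 | 4.30% | 3.47 |
| 0.02 | 0.02 | 26.91% | 6.61% | 4.07 | 8.40% | 3.20 |
| 0.05 | 0.03 | 47.40% | 15.33% | 3.09 | 19.24% | 2.46 |

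The first and last rows give the extremes of the grid. The 30-day window after last dose hardly matters: in a simulation at h = d = 0.01 the visit-based ratio was 4.80 with it and 4.83 without.

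**Step 3: early events.** If the risk is confined to months 0 to 3 (h = 0.02, d = 0.02), the same formulas truncated at 3 months give 5.7% against 5.1%, a ratio of 1.1.

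**Step 4: small numbers.** At h = 0.01, d = 0.02 the expected placebo count is 25 × 0.0337 = 0.84, and the chance of no event is (1 − 0.0337)^25 = 42%. One event in 25 has an exact 95% CI of 0.1 to 20.4%.

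**Step 5: would cutting at Day 140 be enough?** Not with crude percentages. At h = d = 0.01 they would be 4.4% and 3.4% (ratio 1.28), because PSA-triggered switching still shortens placebo time inside the window. Kaplan-Meier with censoring at the switch targets 1 − exp(−0.01 × 4.60) = 4.5% in both arms.

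**The case against.** The strongest reply is that nothing depends on these tables. The objective is to evaluate safety, not to compare it; the analysis is descriptive; and protocol 9.3.2 allows comparisons only where they suit. The Placebo column is labelled as ending at cross-over, and exposure is tabulated. Laboratory values and blood pressure are summarised at each scheduled time point (protocol 9.3.2), so part of the safety data is already time-matched. Crude percentages are also what the protocol mainly reports for the earlier study, whose findings this one is meant to validate, so they must stay.

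Most of this stands, and it is why the point is minor. It does not remove the gap. Separate columns prevent contamination but do not equalise time at risk, and a reader cannot recover AE incidence over a common period from a duration table.

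Three stronger readings are tempting but unsupported:
- *Any apalutamide excess is an artefact.* Protocol 2.2 names rash, fall, weight decrease, arthralgia and fracture as more frequent after exposure adjustment, and describes rash as an early event.
- *Ratios well above 5.* These need no discontinuation for up to 37 months, although treatment stops at metastasis or toxicity, or need switching between visits, although the schedule ties switching to visits.
- *Placebo participants stop treatment less often, going by the 15% and 7.3% AE-related discontinuations in the earlier study.* Those are crude percentages over unequal exposure. Divided by median exposure they are about 15/32.9 = 0.46% and 7.3/11.5 = 0.63% per month, which reverses the direction.

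**Conclusion.** The point holds as a minor one. Followed as written, the plan gives a Placebo versus Apalutamide AE contrast that is misleading for AEs with persisting risk. With no drug effect, the expected percentage ratio is about 3.1 to 5.1 with visit-based switching, and about 2.5 at the low end if all placebo participants complete 5 cycles. This rests on the assumed hazards, 1 to 3% monthly discontinuation, uniform accrual and exponential placebo TTPP; the documents give no AE hazard or mean exposure for this trial. The figures are ratios of expectations, not forecasts of what a table with about 25 placebo participants would show. Early-onset AEs are little affected. The distortion runs against apalutamide, and the TTPP analysis is unaffected.

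**What to change.** In SAP 6.1:
1. Keep the crude tables. Add a footnote that the full-period Placebo and Apalutamide percentages are not comparable, because time at risk differs.
2. Add one Placebo versus Apalutamide table for the overall AE categories and AEs of special interest. Give Kaplan-Meier cumulative incidence of first onset from first dose to Day 140, with 95% CIs and numbers at risk. Censor placebo participants at their first apalutamide dose, and anyone who stops drug at 30 days after last dose.

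Person-time rates over the full period are a weaker choice: they assume a constant hazard and can hide early toxicity.

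The cost is one table and one footnote from data already collected. The new table will have wide CIs, since placebo supplies at most 25 × 4.60/12 = 9.6 patient-years. It should therefore not be extended to single preferred terms generally. Censoring at a PSA-triggered switch may be mildly informative, and the window gives no controlled information on late events.

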6.2. Clinical Laboratory Tests

The number and percentage of subjects with abnormal laboratory values will be summarized. The number and percentage of subjects with parameters with predefined NCI-CTCAE (version 4.03)

toxicity grades of \geq 3 may also be summarized. For selected key laboratory measurements, changes in toxicity grade from baseline to the worst grade experienced by the subject during the Treatment Phase and the Study will be summarized using shift tables.

A listing of subjects who develop toxicities of Grade ≥ 3 will be provided for each laboratory parameter.

6.3. Vital Signs and Physical Examination Findings

Each vital sign (temperature, blood pressure (systolic and diastolic), respiration rate, and heart rate) at baseline will be summarized and presented by treatment group. The number and percentage of subjects with values beyond clinically important limits (defined in Table 2) will be summarized.

Table 2 Clinically Significant Abnormality For Vital Signs

Parameter	Criteria	
Systolic blood pressure	 Absolute result > 160 mmHg and increase from baseline of > 20 mmHg Absolute result < 90 mmHg and decrease from baseline of > 20 mmHg 	
Diastolic blood pressure	 Absolute result > 100 mmHg and increase from baseline of > 10 mmHg Absolute result < 50 mmHg and decrease from baseline of > 10 mmHg 	
Weight	 5 - < 10% weight loss from baseline 10 - < 20% weight loss from baseline >= 20% weight loss from baseline 	

Abnormal findings in physical examination will be recorded and summarized as AEs.

6.4. Electrocardiogram

Electrocardiogram parameters will be summarized using descriptive statistics at baseline.

7. PHARMACOKINETICS/PHARMACODYNAMICS

Descriptive statistics including arithmetic mean, SD, geometric mean, coefficient of variation, median, range will be used to summarize plasma apalutamide and N-desmethyl apalutamide concentrations at each sampling time point.

Individual PK parameters and exposure information of apalutamide and N-desmethyl apalutamide will be derived using population PK modelling. Exposure-response (ER) analysis between exposure and selective clinical endpoint will be explored if deemed necessary and with sufficient data. Details will be given in a separate population PK and ER analysis plan. Results of these analysis will be provided in a separate report.

REFERENCES

- Kaplan EL and Meier P. Nonparametric estimation from incomplete observations. J Am Stat Assoc 1958; 53:457-81
